12. STATISTICAL METHODS

Describe the planned statistical methods including specific tests (e.g., parametric and non-parametric tests, estimation of incidence and prevalence rates, odds ratios, survival/failure analyses, intent to treat analyses). Provide the power calculations used to estimate the proposed sample size. If needed, please consult a biostatistician. (Note: Biostatistical consults are available through Harvard Catalyst.)

Response:

Audio recordings will be de-identified, randomized and blindly rated to count the voice breaks as well as to quantify harshness, breathiness, tremor, and hoarseness using a visual analog scale with three gradation indicators along a 100-mm line (normal, modulates voice, offsets voice), with distance in mm denoting the degree of deviancy from normal, as described earlier (Kirke et al., 2016). Alcohol Challenge Test. All individual measures before and after alcohol intake will be compared using the equation ((Baseline-Alcohol Challenge)/Baseline) \times 100%. To account for potential subjective bias and ensure reliable alcohol effects on voice symptoms, we will consider patients with \geq 10% change of their symptoms from baseline as responsive to alcohol (ETOH+) (Haubenberger et al., 2013; Voller et al., 2014). As a secondary outcome, we will compute Pearson's correlations between symptom scores and brAC measures to examine the baseline and each time point in respect to alcohol content at a corrected p \leq 0.05.

Analysis. The primary outcome within each group will be examined using a linear mixed effect model with treatment (sodium oxybate and placebo) and treatment visits as interacting fixed effects and a per subject random effect at overall $p \le 0.01$ to correct for multiple comparisons. If the interaction between the fixed effects is significant, the difference between treatments will be tested using linear contrasts of least-squares means for the fitted model at $p \le 0.05$ adjusted for multiple comparisons. As a secondary analysis, benefit ratio will be calculated as (sodium oxybate effect – placebo effect) and analyzed using a Friedman test at $p \le 0.01$.

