1. STUDY SUMMARY

Provide a brief summary of the proposed research (in language that can be understood by a non-scientist).

Response: Spasmodic dysphonia, or laryngeal dystonia, is a chronic debilitating condition that selectively affects speech production due to involuntary spasms in the laryngeal muscles. SD often extends beyond vocal communication impairment and causes significant occupational disability and life-long social isolation. SD becomes even more incapacitating when it is associated with dystonic voice tremor (VT), which is present in about 1/3 of SD patients and is characterized by the inability to sustain a vowel for more than a few seconds. Current treatment of these disorders is limited to the temporary management of voice symptoms with repeated injections of botulinum toxin into the laryngeal muscles, which, however, are not effective in all SD patients and even less so in combined SD/VT cases. There is, therefore, a critical need to identify alternative therapeutic options that are specifically targeting the pathophysiology of SD and VT. On the other hand, the design and use of such novel therapeutic approaches will be largely unattainable if their central mechanisms of action remain unknown. Our long-term goal is to determine the pathophysiology of SD and related disorders, such as VT, and develop new diagnostic and treatment options for these patients. The objective of this application is to elucidate the primary determinants of clinical response to a novel oral medication, sodium oxybate (Xyrem®), in alcohol-responsive SD and SD/VT patients. This research is innovative because it will use a controlled experimental design that focuses on detailed characterization of primary effects of a novel oral medication, sodium oxybate, for treatment of SD and VT symptoms. The proposed research is significant because it is expected to have broad translational impact on improving the clinical management of patients with SD and VT, opening new therapeutic horizons for treatment of these and similar disorders.

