2. SPECIFIC AIMS

List the specific aim(s) and objective (s) of the study (i.e., what does the study hope to accomplish). Include any secondary and exploratory aims and objectives (e.g., biomarkers, genetic analyses).

Response: Determine the clinical response of SD and VT symptoms to sodium oxybate.

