Significance of the Expected Research Contribution. Our contribution here entails the detailed understanding of the primary contributing factors that underlie the clinical benefits of sodium oxybate in ETOH+ SD and SD/VT patients. Our rigorous experimental approach will include symptom evaluation based on the objective alcohol challenge test and double-blind, placebo-control, randomized, cross-over study design to identify the primary determinants of sodium oxybate response in ETOH+ SD and SD/VT patients. The expected outcome of these studies will allow for translations from bedside to bench and bedside again, maximizing integration between clinical and basic aspects of this research program. Collectively, the proposed studies have strong scientific premise because they will allow for delineation of the mechanistic aspects of sodium oxybate's effects on SD and VT pathophysiology. As such, successful completion of the proposed studies will establish a muchneeded scientific rationale for the future large clinical trials and the ultimate use of sodium oxybate as a therapeutic option for treatment of SD and VT. This will be especially important for those patients who have suboptimal response to botulinum toxin treatment or forgo it due to personal or medical issues. Thus, this contribution will be significant because it is expected to have a broad translational impact on improving the clinical management of patients with SD and VT. It is further expected that our findings will be equally applicable to the treatment of other forms of ETOH+ dystonia and dystonic tremor. Taken together, the proposed rigorous experimental approach to identify an effective oral medication for SD and SD/VT based on disorder pathophysiology will represent a significant departure from the existing trial-and-error attempts to treat these disorders. It will represent a novel therapeutic approach directed to the treatment of the disorder per se rather than temporary management of voice symptoms as with the current use of botulinum toxin.

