Enrollment and Eligibility Screening. Patient eligibility will be established based on the initial screening interview and the review of medical information, including laryngological and neurological examinations. Any subject with neurological (other than SD or dystonic VT in the patient groups), laryngeal, or a history of psychiatric problems will be excluded from the study. All patients will be right-handed, native English speakers according to the standardized Edinburgh Handedness Inventory (Oldfield, 1971), which will be important in examining drug-induced central effects during speech production. Because brain and laryngeal surgery may influence functional brain organization, all patients with a history of brain and/or laryngeal surgery will be excluded from the study. To avoid the possibility of confounding effects of drugs that act upon the central nervous system, patients who receive any medication(s) affecting the central nervous system will be excluded from the study. All patients will be asked to abstain from consuming any alcohol or caffeine (or foods with caffeine such as chocolate) for at least 48 hours before the study visits.

General Study Procedures. Eligible patients will require three visits, including one for the alcohol challenge test and two for sodium oxybate and placebo treatments (**Fig. 1**). At their initial baseline, all patients will be assessed for vital signs (blood pressure, pulse, height and weight); cognitive and

[figure not shown]

Fig. 1. Flowchart of study procedures. ETOH+ alcohol-responsive; ETOH- alcohol-non-responsive.

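### The protocol sets out to find what determines response to sodium oxybate, but no analysis in section 12 relates any patient-level variable to the oxybate-minus-placebo response

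*Combined protocol and SAP*

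**What the plan says.** The objective appears twice. Section 1 says the purpose is to "elucidate the primary determinants of clinical response to a novel oral medication, sodium oxybate", in alcohol-responsive patients. Section 3 says the design is meant to "identify the primary determinants of sodium oxybate response in ETOH+ SD and SD/VT patients". Section 2 lists a narrower aim: "Determine the clinical response of SD and VT symptoms to sodium oxybate". The hypothesis in section 11 is a contrast: the drug works in EtOH+ patients and not in EtOH- patients.

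Section 12 expresses the alcohol challenge result as percent change from baseline and then applies the cut: patients with at least a "10% change of their symptoms from baseline as responsive to alcohol (ETOH"+). For the trial itself, "The primary outcome within each group will be examined using a linear mixed effect model" whose fixed effects are treatment, visit and their interaction, with a random subject effect. Two further analyses are named. One is a set of Pearson correlations between symptom scores and breath alcohol. The other is a Friedman test on the oxybate effect minus the placebo effect.

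Section 10 gives secondary and exploratory outcomes as not applicable, and section 11 states no secondary hypothesis.

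**The concern.** A claim about what determines response needs an analysis with the drug effect on one side and a patient characteristic on the other. Section 12 has none. A patient who improves by 9% after alcohol is classed with one who worsens, and a patient at 11% with one at 60%. Because the models are fitted group by group, even the two-class version of alcohol response is never tested as a modifier. A significant result in one group beside a non-significant result in the other is not such a test.

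At stake is what the trial can report. As planned it yields separate within-group drug effects. It cannot say how strongly alcohol response predicts drug response, although the challenge is run in every patient. A model added after unblinding would make the answer to the stated objective post hoc.

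**Working it through.** **1. The plan's own figure.** Section 5 states 22 patients for 80% power at 0.0125, from a response rate of 37/45 = 0.822. The null rate and sidedness are not stated; I assume 0.5 and one-sided. With n = 22 the exact binomial test rejects at 17 or more: P(X ≥ 17 | 0.5) = 0.0085 and P(X ≥ 17 | 0.822) = 0.816. The figure reproduces, with 22 the smallest n to reach 80%. It is a within-cohort calculation and gives no power for any question about determinants.

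**2. What each analysis in section 12 relates.**

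| Analysis | Outcome | Predictor |
|---|---|---|
| Percent change and 10% cut | symptoms after alcohol | none (classification) |
| Pearson correlations | symptom scores | breath alcohol |
| Mixed model, per group | symptoms | treatment, visit |
| Friedman test | oxybate minus placebo | no patient-level predictor named |

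No row has drug response as outcome and a patient characteristic as predictor.

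**3. Inside the ETOH+ group.** Sections 1 and 3 word the objective for alcohol-responsive patients. There the indicator I(change ≥ 10%) equals 1 for everyone, so its variance is 0 and it cannot explain variation in response. This needs no distributional assumption.

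**4. Cost of the cut if the relation is linear.** The efficiency of the cut relative to the continuous variable is the squared correlation of X with I(X ≥ c). For normal X with a share p above the cut it is φ(z_p)² / [p(1−p)].

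| Share ETOH+ | Efficiency | Loss |
|---|---|---|
| 50% | 0.637 | 36% |
| 70% | 0.576 | 42% |
| 80% | 0.490 | 51% |

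At 50%: 0.3989² / 0.25 = 0.637. So 140 patients (4 × 35) are worth 140 × 0.637 = 89, and 88 completers (4 × 22) are worth 56.

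Other shapes lose less. A uniform variable split evenly loses 25%. Equal mixtures of non-responders centred at 0% (SD 5 to 10) and responders centred at 20% to 50% (SD 10 to 15) lose 11% to 33%.

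**5. Cost if benefit is a step at 10%.** With no measurement error the roles reverse: the cut is the correct predictor and the continuous coding is the inefficient one. I simulated 88 patients, alcohol response with mean 12% and SD 20%, residual SD 25, two-sided 5%, and either a slope of 0.35 or a step of 14 at 10%. All of these values are assumptions.

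| True relation | Error SD in alcohol response | Power, continuous | Power, cut |
|---|---|---|---|
| Linear | 10 | 63% | 44% |
| Step | 10 | 43% | 43% |
| Step | 5 | 50% | 57% |
| Step | 0 | 53% | 73% |

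At the 0.01 level that section 12 uses for the primary model, the linear case gives 38% against 21%.

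**6. Is the continuous predictor defined?** Not yet. Section 12 applies the formula to every measure. There are five: voice breaks, harshness, breathiness, tremor and hoarseness. Section 9 lists five post-alcohol times (15, 30, 45, 60 and 120 min). That allows 5 × 5 = 25 percent changes per patient, with none singled out.

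**The case against.** The best defence is that the listed aim and the hypothesis concern response in two groups, that the 10% rule is prespecified with a stated reason and cited precedent, and that a group contrast suits a step-like effect. Much of this stands. The cut is legitimate for classification, and under a step it costs nothing. But the narrower aim in section 2 does not withdraw the objective in sections 1 and 3, and even the group contrast has no test in section 12.

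Three stronger readings are tempting and go too far:

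- **That alcohol response is the only determinant in the design.** Section 5 counts four cohorts and section 9 names ETOH+ and ETOH- patients, each with SD and SD/VT, so diagnosis appears to be a second grouping factor. It is still not a term in any model.
- **That the cut throws away a third to a half of the information.** This assumes a linear relation, and a half also needs a split near 80:20. The documents give neither. Recruiting by self-reported alcohol effect points to a fairly even and possibly two-peaked variable: 70 and 70 if the four cohorts are alcohol group by diagnosis. The 82.2% in section 5 is the oxybate response rate among ETOH+ patients, not the ETOH+ share.
- **That a fitted slope would be conservative.** Error in the alcohol response usually pulls a slope towards zero. Here baseline severity is in the denominator of the percent change and may also drive the size of the drug effect, so the direction of bias is not assured.

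**Conclusion.** The gap is real. The plan as written cannot answer the determinants objective, because no analysis relates a patient-level variable to oxybate-minus-placebo response, and within ETOH+ patients the cut cannot do so in principle. That rests on the text alone.

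The size is conditional: about 36% of the information under a linear relation with an even split of a normal variable, about 11% to 33% with separated subgroups, and none under a step at 10%. Shape, split, slope and noise are assumptions, not figures from the documents. A reader might infer that the 10% rule is itself a mistake or that the within-group tests are invalid; neither follows. What is missing is one analysis.

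**What to change.** Keep the 10% groups and the within-group tests. Add to section 12 one prespecified secondary crossover model over all randomised patients, at the post-dose time used for the primary outcome, with a random subject effect and these terms:

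- treatment and period;
- alcohol-challenge percent change as a continuous variable, and treatment by percent change;
- diagnosis (SD or SD/VT), and treatment by diagnosis;
- baseline severity with its own treatment interaction, because a patient-level main effect drops out of the within-patient contrast.

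Name one symptom measure and one post-alcohol time to define percent change, and say how a zero or very low baseline is handled. Report the treatment-by-alcohol-response slope with its confidence interval, and the ETOH+ against ETOH- contrast beside it, so that a graded and a step-like relation are both visible. Body weight is recorded at baseline ("all patients will be assessed for vital signs (blood pressure, pulse, height and weight") and may enter as an exploratory covariate.

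The cost is a short paragraph, with no new visits or data. The work lies in choosing the measure and the time. The downsides are one more secondary test and a slope that measurement error will usually, though not certainly, weaken. Section 5 gives no power for this model, so it should be presented as estimation.

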Alcohol Challenge Test. To determine the reliability and reproducibility of patients' self-reported benefits from alcohol on voice symptom, all patients will undergo the standardized alcohol challenge test for movement disorders (Knudsen et al., 2011; Haubenberger et al., 2013; Voller et al., 2014). Oral ethanol (40%, by volume) will be administered at a total dose of 0.8 g/L of the calculated total body water. It may be mixed into 50 ml of a sugarless, uncaffeinated drink, such as diet Sprite (Watson, 1989). The same dose of alcohol will be administered for the second time 30 min after the first administration. EPIC will be used for alcohol dispensing to ensure accurate and complete documentation. The alcoholic drink will be supplied by the MEEI Research Pharmacy. The test will be performed within fixed hours between 10am-12pm. The patients will be asked to drink their

predetermined amount of alcohol as fast as possible within 5-10 min. The levels of alcohol will be assessed using breath alcohol content (brAC) readings of the breathalyzer at eight time points, including twice before the alcohol challenge and at 15, 30, 45, 60, 120 min after alcohol intake (Haubenberger et al., 2013; Voller et al., 2014). Audio recording of voice and speech samples will be synchronized with brAC measurements and rated as described above.

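### The planned Pearson correlations of symptom score with breath alcohol are undefined at baseline and, read literally, compare patients with each other afterwards; a within-patient model would suit the question better

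*Combined protocol and SAP*

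**What the plan says.** Section 12 (Statistical Methods, Alcohol Challenge Test) names, as a secondary outcome, Pearson correlations "between symptom scores and brAC measures to examine the baseline and each time point in respect to alcohol content", judged at a corrected p of 0.05. It does not say whether the correlations run across or within patients, which symptom score and which patients enter, or how p is corrected. The scores available are a count of voice breaks and four 100-mm visual analogue ratings.

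Three statements in section 9 (Study Procedures) bear on this:

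- **Abstinence.** Patients are to "abstain from consuming any alcohol or caffeine (or foods with caffeine such as chocolate) for at least 48 hours before the study visits".
- **Dose.** Ethanol is "administered at a total dose of 0.8 g/L of the calculated total body water", and "The same dose of alcohol will be administered for the second time 30 min after the first administration".
- **Sampling.** brAC is read at "eight time points, including twice before the alcohol challenge and at 15, 30, 45, 60, 120 min after alcohol intake", with voice recordings synchronized to the readings. The text announces eight time points but lists seven.

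No power or sample size is given for these correlations.

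**The concern.** A correlation at one time point needs variation in both variables between patients. Before the drink there should be none in brAC. After it, body-water dosing is meant to bring patients to similar levels, while symptom severity differs widely for reasons unrelated to alcohol. If every patient improved by the same amount, each score would shift equally and the cross-sectional correlation at that time would not change. So the statistic responds weakly to the effect it is meant to show.

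This is the only planned analysis that links symptoms to measured alcohol level. A null result could be read as absence of a relation to alcohol when it came from the choice of method.

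**Working it through.** **1. Is there a figure in the plan to reproduce?** Not for this analysis. The 22 patients in section 5 belong to a binomial test of the primary outcome. That figure reproduces with an exact one-sided test of 37/45 against an assumed null of 0.50 at 0.0125 (power 81.6%), but it says nothing about these correlations.

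**2. Baseline.** With 48 hours of abstinence, brAC = 0 for every compliant patient, so its variance is 0. Pearson's r divides by the SD of brAC and is undefined. The only assumption is compliance.

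**3. After intake, raw scores, one time point.** Inputs:

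- From the plan: up to 35 patients per cohort and up to 140 in all (section 5); five listed post-dose times.
- Assumed: between-patient severity SD 20 mm, recording SD 6 mm, brAC CV c = 0.20 to 0.30, a common mean improvement E of 3, 10 or 20 mm at peak, and Bonferroni over five times for one score, so two-sided alpha = 0.05/5 = 0.01.

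Implied size of the across-patient correlation: r = E·c / √((E·c)² + 20² + 6²). Power by Fisher's z: Φ(atanh(r)·√(n−3) − 2.576), plus a negligible opposite tail.

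| E | c | r | power, n = 35 | power, n = 140 |
|---|---|---|---|---|
| 3 mm | 0.20 | 0.6/√436.36 = 0.029 | 1% | 1% |
| 3 mm | 0.30 | 0.9/√436.81 = 0.043 | 1% | 2% |
| 10 mm | 0.20 | 2/√440 = 0.095 | 2% | 7% |
| 10 mm | 0.30 | 3/√445 = 0.142 | 4% | 18% |
| 20 mm | 0.20 | 4/√452 = 0.188 | 7% | 36% |
| 20 mm | 0.30 | 6/√472 = 0.276 | 17% | 77% |

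Simulation agrees: about 1%, 2–4% and 5–18% at n = 35, and up to 79% in the most favourable cell at n = 140. For comparison, the smallest r detectable with 80% power at alpha 0.01 is tanh((2.576 + 0.842)/√32) = 0.54 at n = 35 and tanh(3.418/√137) = 0.28 at n = 140.

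**4. Change scores instead of raw scores.** Subtracting the mean of the two baseline recordings removes severity and leaves noise variance 36 + 36/2 = 54. For E = 10 mm, r = 2/√58 = 0.263 (c = 0.20) or 3/√63 = 0.378 (c = 0.30). Power at n = 35 is 15% or 37% by formula, and about 15–40% by simulation.

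**5. Within-patient slopes, same alpha 0.01.** Regress each patient's seven scores on that patient's brAC, then test the mean slope. The brAC time course is not in the documents. Take, as an assumption, 0, 0, 0.4, 0.5, 0.9, 1.0 and 0.7 of peak. Its mean is 0.5 and its sum of squared deviations is 0.96. The SE of the mean slope at n = 35 is about 6/√0.96/√35 = 1.04 mm. So 3 mm is about 2.9 SE and 10 mm about 9.7 SE. Simulated power, allowing for variation in brAC, is about 42–53% for 3 mm and about 100% for 10 mm or more. The 3 mm figure moves somewhat with the assumed time course.

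**6. All times pooled in one correlation.** Here r is defined, because brAC varies over time. But seven recordings from one patient are treated as independent, and severity is counted as noise. Simulated type I error is about 1% at nominal 5% (CV 20%). Power at nominal 5% and n = 35 is 91% for 10 mm, but 8% for 3 mm against 76% for within-patient slopes at the same 5%.

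**The case against.** The strongest reply is that section 12 does not commit to the unfavourable reading. It states no unit of analysis. The same paragraph first defines percent change from baseline for all individual measures, so the scores could be change scores, and the sentence could also mean pooling all times. All patients take the alcohol challenge, so up to 140 could enter rather than 35. No brAC or score variance is documented; narrow brAC spread is an inference from body-water dosing. The alcohol response is classified by the 10% change rule in the same section, not by this correlation.

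All of that stands, and it limits the point. A reader might infer that the correlations can never answer the question, or would nearly always be null even when every patient improves. The documents do not support that: it needs one reading, one cohort and variances they do not give, and in a favourable corner (n = 140, 20 mm, CV 30%) even the raw per-time correlation reaches about 79% power. Pooling responsive and non-responsive patients to reach 140 would, however, dilute a common slope.

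The objection does not rescue the baseline correlation. Nor does it offer a reading that matches the within-patient analysis for a single cohort: change scores are weaker, and pooling has the wrong error rate.

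**Conclusion.** The point holds as a matter of method. The baseline correlation is undefined in compliant patients. The literal per-time correlation mainly compares patients with each other, and a within-patient analysis of the same recordings addresses the stated aim better.

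The size is conditional on the assumed SDs, brAC spread, common slope, time course and five-test correction. For one cohort of 35 and a 10 mm effect at alpha 0.01, the comparison is 2–4% (raw), about 15–40% (change score) and about 100% (within-patient slope).

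A reader might also infer that the trial's main conclusions are at risk. They are not: this is a secondary analysis that feeds neither the assignment to alcohol-responsive or non-responsive groups nor the primary mixed model. It is worth correcting because a null result could be misread and the correction is cheap.

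**What to change.** In section 12, replace the correlations with one linear mixed model of symptom score on time-varying brAC over all synchronized recordings, with a random intercept and slope for patient. A one-sample test of the within-patient slopes is a simpler alternative. Report the mean slope with its confidence interval. Keep the pre-drink recordings as the zero-brAC anchor and drop the baseline correlation.

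State which score or scores are modelled, which patients enter (with responsive and non-responsive groups separate or as a term in the model), and what family of tests the correction covers. Reconcile the eight announced time points with the seven listed, and section 10(b), which gives secondary outcomes as not applicable, with section 12, which names this one.

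The cost is SAP wording. No new data are needed, and the plan already uses a mixed model with a per-subject random effect for the primary outcome.
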